11.6.2 TREATMENT PERIOD

The approximately 19-week Treatment Period (18 weeks for Dose Expansion Cohort) includes approximately 27 scheduled clinic visits Day 1 [baseline], Day 7 of NOX66 monotherapy (Dose Escalation part), Days 1 and 2 of Treatment Cycles 1 to 6 of combined NOX66 and doxorubicin as well as Days 9 and 16 of Cycle 1 and the other subsequent 5 cycles. Scheduled follow-up assessments will occur at Months 6, 9, 12, 15, and 18 (End of

Study) from Cycle 1 Day 1. Additional follow-up visits may be conducted at any time during study participation per Investigator's discretion based on the type and severity of any notable safety finding as well as evaluation of any doxorubicin-induced toxicity (i.e., myelosuppression) that can delay the next dose of doxorubicin or result in a dose reduction.

There is a window of ± 1 day around scheduled study visits on Day 7 of NOX66 monotherapy and Day 2 of Cycles 1 to 6. A ± 1 day window may also be utilized in the event of scheduling conflicts due to public holidays. A 7-day window is acceptable for all other visits during the follow-up period (Months 6, 9, 12, 15 and 18).

Telephone contact between the site staff and the patient is to be encouraged between study visits to assess compliance, tolerability of the study drug. Sufficient study drug for a 7-day period will be dispensed to the patients.

11.6.2.1 Monotherapy Period (Days 1 to 6) – Only for dose escalation

Eligible patients who are enrolled and wish to continue will return to the study site in the morning on Day 1 and the following will take place:

- Record changes in medical history including any changes in concomitant medications since screening (Section 10.4).
- Measure vital signs (blood pressure, pulse [radial or brachial (to be measured over 30 seconds if performed manually)], respiration rate and body temperature [oral or aural]; Section 11.4.2.1).
- Perform a physical examination (including weight; Section 11.4.2.2).
- Obtain a triplicate 12-lead ECG after 5 minutes of rest in the supine position at -0.75, -0.5 and -0.25 hours prior to administration of NOX66.
- Collect urine and fasting blood samples for clinical laboratory tests (Table 3). ANC should be $> 1000/\mu\text{L}^3$ prior to study drug administration.
- Collect blood samples for genetic mutations, levels of BNP, troponin I, cytokines, chemokines and immunoassays prior to NOX66 administration. (These samples can be collected during Screening, if needed, at the end of all Screening assessments)
- Females of childbearing potential will undergo a urine pregnancy test (per inclusion criteria [Section 9.2, negative results must be obtained prior to dosing with study drug]). A window of -1 day is acceptable.
- Collect PK pre dose blood sample within 15 minutes prior to administration of NOX66.
- Administer questionnaires BPI-SF, EORTC QLQ-C30 and EORTC QLQ-FA12. Assess and record AEs and update medical history (Section 16).
- Review inclusion/exclusion criteria (Sections 9.2 and 9.3).

Once eligibility is confirmed, the following will occur:

- Instructions for self-administration of study drug will be reviewed with the patient and/or a household member who has agreed to administer NOX66.

- The individualized doses will be determined based on the cohort to which they are assigned. The frequency of dosing will be BID or TID beginning on Day 1.
- Patients will be given an adequate supply of study drug for 7 days administration.

The study drug will be self-administered by the patient; the patient will then undergo the following assessments:

- On Day 1, PK blood sampling at 1, 2, 3, 4, 6, 8, and 24 hours post first dose. The 24-hour sample may be taken at home or in the clinic on Day 2, prior to NOX66 administration.
- On Day 1, record triplicate 12-lead ECG at 1, 2, 5, and 8 hours after the first dose of NOX66. As noted in Section [11.4.3](#), ECGs are to be taken prior to the blood sample collection.
- On Day 1, assess and review TEAEs (Section [16](#)).
- On Day 1 dispense a diary to record times of drug administration for Days 2 to 7.
- On Day 1, instruct patients to return to the study site at Day 7 with completed diary and not to take the morning dose of NOX66 on Day 7 at home.

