	
 • Complete blood count • Electrolytes (Ca⁺⁺, Mg⁺⁺), PO₄, BUN, creatinine 
The following criteria will be used to evaluate the efficacy of NOX66 alone and in combination with doxorubicin:
 
 • RECIST v1.1: Disease Control Rate (DCR) defined as [(stable disease (SD) + partial response (PR) + complete response (CR)/All)], overall response rate (ORR) • Overall survival (OS), Progression Free Survival (PFS) • European Organization for Research and Treatment of Cancer: Core Quality of Life Questionnaire v3.0 (EORTC QLQ-C30) • Fatigue Severity Scale (European Organisation for Research and Treatment of Cancer: Cancer Related Fatigue Module - EORTC QLQ-FA12) • Brief Pain Inventory (short form) • Suppository Acceptance Questionnaire 
The following criteria will be used to evaluate the PK of idronoxil and metabolites in blood plasma after single and repeated doses of NOX66:
 
 • Maximum concentration (C_{max}) • Time to reach maximum concentration (T_{max}) • Trough concentrations after repeated administration • Area under the concentration-time curve up to last measurable time point and infinity (AUC_{last} and AUC_{inf}) • Area under the concentration-time curve over a dosing interval after repeated administration (AUC_T) • Terminal elimination half-life (if possible) 
Pharmacokinetic parameters of idronoxil and metabolites obtained on Day 7 will be compared to Day 1 values. Sparse PK sampling for determination of idronoxil and metabolites, doxorubicin and doxorubicinol concentrations will be obtained during the treatment cycles to assess variability of exposure of idronoxil and doxorubicin in an exploratory manner.
 
The following biomarkers will be evaluated to assess the relationship between response to NOX66 and doxorubicin:
 
 • Genetic mutations • Change in lipid profile from baseline • Cytokine/chemokine and ENOX2 dynamics
Number of Patients (Planned)	Up to approximately 34 patients with metastatic soft tissue sarcoma will be studied if the MTD is determined with the maximum dose planned for this study. If a minimum number of patients is studied per dose escalation, the expected number of patients is approximately 28.

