7.2 SECONDARY OBJECTIVES

- To determine single-and multiple-dose pharmacokinetics (PK) of idronoxil
- To determine the preliminary efficacy and quality of life (QOL) of the MTD of NOX66 in combination with doxorubicin.

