10.2 INVESTIGATIONAL PRODUCT ADMINISTRATION

10.2.1 ADMINISTRATION

Depending on the cohort/dose level, 2 to 3 suppositories will be self-administered daily for 7 days in the Monotherapy period (only for Dose Escalation part) and/or in combination with doxorubicin for the treatment cycles. In this study, the dosage forms will be inserted rectally either twice (12 hours apart) or three times (8 hours apart) per day. In patients who have regular bowel movements (i.e. within several hours after awakening) patients will be instructed to insert the suppository after the bowel movement. To promote regular movements, patients should be encouraged to consume a high fiber diet, with adequate amounts of water. In those patients who are not on a regular bowel movement schedule, insertion of the suppository should occur at regularly scheduled times individualized for the patient. If defecation occurs after NOX66 administration, no re-dosing is required. The next dose should be administered at the scheduled time. During the NOX66 and doxorubicin combination treatment cycles, if diarrhea occurs, the Investigator must follow standard management practices to manage the diarrhea to allow for NOX66 administration.

If any patients have difficulty with administering suppositories three times per day (8 hours apart) due to any personal reasons, dosing schedule can be changed to two times daily (3 suppositories per day) after Cycle 2. In this instance, patients can administer one 600-mg suppository in the morning and two 600-mg suppositories in the evening. While two suppositories are administered, each suppository needs to be inserted at least 5 minutes apart.

The dosing time for each suppository must be recorded by the patient in a diary which must be brought to the clinic at each visit. The dose escalation scheme is presented in [Table 1](#)

Proposed Starting Dose and Dose Escalation Scheme for NOX66

Table 1 Proposed Starting Dose and Dose Escalation Scheme for NOX66

Cohort	1	2	3
Increment	NA	50%	50%
Total daily dose (mg)	800	1200	1800
Daily regimen (mg)	400 BID	600 BID	600 TID

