11.1.2 SECONDARY ENDPOINTS

11.1.2.1 Pharmacokinetics

Blood concentrations of idronoxil and idronoxil metabolites and plasma concentrations of doxorubicin and doxorubicinol will be assayed by validated methods by a central laboratory. PK parameters of idronoxil and metabolites, will be determined using non-compartmental analyses after administration of idronoxil on Days 1 and 7 during monotherapy in the Dose Escalation Part and include:

- C_{\max} Maximum observed blood drug concentration
- T_{\max} Time to reach C_{\max}

- AUC_{last} Area under the blood concentration time curve (AUC) from time 0 to the last measurable concentration
- AUC_{τ} AUC from time 0 to end or dosing interval (τ)
- AUC_{inf} AUC from time 0 to infinity (if possible)
- kel^a Terminal elimination rate constant, calculated from a semi-log plot of the blood concentration versus time. The parameter will be calculated by linear least squares regression analysis using the maximum number of points in the terminal log-linear phase (e.g., 3 or more nonzero blood concentrations).
- $T_{1/2a}$ Terminal elimination phase half-life, calculated as $0.693/kel$ (if possible)

^aNote: No value for kel, or $T_{1/2}$ will be reported for cases that do not exhibit a terminal log linear phase in the concentration versus time profile. Additional blood PK parameters may be calculated if deemed appropriate.

For the Dose Escalation Part, during the combination cycles, 1 to 4 PK samples will be obtained on Days 2, 7, and 8 to assess concentrations of idronoxil and metabolites or doxorubicin and doxorubicinol. For the Dose Expansion Part, 1 to 3 PK samples will be obtained on Days 2 and 7 to assess concentrations of idronoxil and metabolites or doxorubicin and doxorubicinol. Comparisons will be made to assess the degree of inter-and intra-patient variability during the study.

At the discretion of the Sponsor, non-evaluable concentrations or parameters may be excluded from the final PK analysis dataset. Any data exclusions will be documented in the final study report. The relationship between PK parameters and adverse events and other safety findings will be explored.

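### Day 1 AUClast is meant as a single-dose measure but runs to a 24-hour sample taken after two (BID) or three (TID) doses

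*Combined protocol and SAP*

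**What the plan says.** Section 7.2 lists as a secondary objective "To determine single-and multiple-dose pharmacokinetics (PK) of idronoxil". The Synopsis plans a separate summary for single-dose samples and says that PK parameters "obtained on Day 7 will be compared to Day 1 values".

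On dosing, Section 11.6.2.1 states "The frequency of dosing will be BID or TID beginning on Day 1", and Section 10.2.1 states that "the dosage forms will be inserted rectally either twice (12 hours apart) or three times (8 hours apart) per day".

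On sampling, Section 11.6.2.1 states "On Day 1, PK blood sampling at 1, 2, 3, 4, 6, 8, and 24 hours post first dose" and adds "The 24-hour sample may be taken at home or in the clinic on Day 2, prior to NOX66 administration". Section 11.4.3 and footnote 8 of Table 4 also list 24 hours as a post-dose time for Day 1.

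On parameters, Section 11.1.2.1 plans non-compartmental analysis on monotherapy Days 1 and 7. AUClast is defined as "Area under the blood concentration time curve (AUC) from time 0 to the last measurable concentration". AUCinf and half-life are to be reported where possible, and kel and half-life only when there is a log-linear terminal phase. Nothing in Section 11.1.2.1 or 14.3.9 ends the Day 1 profile at the second dose or restricts the 24-hour sample to use as a trough.

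**The concern.** A single-dose AUC should cover the period when only one dose has been given. Here the last interval of the trapezoid, 8 to 24 hours, spans one further dose (BID) or two (TID). Their peaks are unsampled, but their residue raises the 24-hour value.

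This matters in two comparisons. Day 1 is the reference for Day 7, so an inflated Day 1 value understates accumulation. Between dose levels, Cohort 2 (600 mg BID) and Cohort 3 (600 mg TID) take the same first dose, so their single-dose exposure should agree apart from patient variability. AUClast as defined would separate them because of the number of doses taken.

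**Working it through.** **1. Timeline.** Doses are 12 or 8 hours apart (Section 10.2.1).

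| Regimen | Day 1 doses (h) | Samples (h) | Doses before the 24-h sample |
|---|---|---|---|
| BID | 0, 12 | 0, 1, 2, 3, 4, 6, 8, 24 | 2 |
| TID | 0, 8, 16 | same | 3 |

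The 24-hour sample is 24 − 12 = 12 h after the last BID dose and 24 − 16 = 8 h after the last TID dose. This step needs no assumption beyond the stated schedule.

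**2. Model for size.** The plan gives no figure to reproduce, and the documents give no absorption rate or half-life for idronoxil, so both are assumed. For unit dose over volume, with Δ the time since each dose, the concentration is the sum over doses of ka/(ka − ke) × (exp(−ke·Δ) − exp(−ka·Δ)), where ke = ln 2 / half-life. AUClast is the linear trapezoid over the protocol's times.

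**3. Worked case: ka 1/h, half-life 4 h.** The trapezoid from 0 to 8 h is 3.948 in every regimen, and the 8-h concentration is 0.302. The true single-dose AUC0-24 is 5.662.

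- One dose only: 24-h level 0.0189. AUClast = 3.948 + 16 × (0.302 + 0.0189)/2 = 6.515. Ratio to true 1.15.
- BID: 24-h level 0.1701. AUClast = 3.948 + 16 × (0.302 + 0.1701)/2 = 7.725. Ratio 1.36.
- TID: 24-h level 0.3965. AUClast = 3.948 + 16 × (0.302 + 0.3965)/2 = 9.536. Ratio 1.68.
- TID over BID = 9.536/7.725 = 1.23.

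The one-dose line isolates the error from having no sample between 8 and 24 h. It is the same for both regimens, so the difference between TID and BID comes from dose count.

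**4. Range at ka 1/h** (AUClast divided by true single-dose AUC0-24).

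| Half-life (h) | One dose, sparse sampling | BID | TID | TID/BID |
|---|---|---|---|---|
| 1 | 1.01 | 1.01 | 1.07 | 1.06 |
| 2 | 1.15 | 1.21 | 1.43 | 1.18 |
| 4 | 1.15 | 1.36 | 1.68 | 1.23 |
| 6 | 1.10 | 1.38 | 1.72 | 1.25 |
| 8 | 1.07 | 1.38 | 1.72 | 1.25 |

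With slower absorption (ka 0.4/h) and half-life 2 to 8 h, TID over BID is 1.25 to 1.27.

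**5. Half-life if the 24-hour point is used.** Regressing log concentration on time at 6, 8 and 24 h (ka 1/h), BID gives 6.7 h for a true 2 h, 15.4 h for a true 4 h and 83 h for a true 8 h. TID gives 36 h for a true 2 h. From a true 4 h upward the TID slope is positive and there is no half-life.

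**6. What truncation at 8 h recovers.** Cmax, Tmax and AUC0-8 describe one dose. At ka 1/h, half-life from the 4, 6 and 8 h samples is 1.1 to 13.3 h for a true 1 to 12 h. AUCinf is 0.96 to 1.07 times true, with 1 to 69% of it extrapolated. At ka 0.4/h, AUCinf is 1.30 times true at a half-life of 4 h and 2.50 times at 8 h.

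**The case against.** **Half-life and AUCinf.** A reader might infer from step 5 that these are bound to be wrong. The documents do not support that. Section 11.1.2.1 admits only points in the log-linear phase and otherwise reports no kel or half-life. A sample taken after later doses is not on the first dose's terminal phase, and a positive TID slope yields nothing. What remains is that the 24-hour point is not expressly excluded, and a BID profile can still decline through it. These safeguards do not reach AUClast. The sponsor's discretion to drop non-evaluable data has no stated criterion.

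**AUC over the dosing interval.** A reader might also infer that AUCtau for BID cannot be obtained without a 12-hour sample. The Synopsis defines AUCtau after repeated administration. For Day 7 there is a pre-dose sample and a Day 8 sample 12 h after the last dose, which supply the trough at steady state. The gap affects only a Day 1 BID value, which Section 11.1.2.1 does not separate from Day 7.

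**Conflicting text.** The Synopsis and the Table 7 grid stop the Day 1 profile at 8 h and show the next sample as a Day 2 pre-dose sample. Section 11.6.1 speaks of one self-administered dose after the baseline evaluations, and the diary in Section 11.6.2.1 starts on Day 2. But Section 11.6.1 does not say that later Day 1 doses are withheld. Section 11.6.2.1 is the more specific text on dosing frequency, and the note under Table 7 itself speaks of a 24-hour sample. The conflict calls for reconciliation and does not remove the problem.

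**Consequence.** PK is secondary and descriptive, in cohorts of 3 to 6, with no planned test between cohorts. Section 14.3.12 defers data-handling rules to a later SAP, which may cover this. That limits the weight of the point. It does not alter the AUClast definition now in the protocol.

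**Conclusion.** The point holds for Day 1 AUClast. As defined, it carries two or three doses into a parameter meant to describe one. Because nothing is sampled between 8 and 24 h, it is not a usable 24-hour multiple-dose exposure either.

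The timeline is certain; the size is illustrative. With ka 1/h and half-life 2 to 8 h the ratio to truth is 1.21 to 1.38 (BID) and 1.43 to 1.72 (TID). Not all of this comes from the extra doses, since sparse sampling alone gives 1.07 to 1.15. The cleaner measure of the dose-count effect is the 18 to 25% by which Cohort 3 would exceed Cohort 2. The bias is small if half-life is about 1 h with that absorption rate (1.01 and 1.07). With ka 0.4/h and the same half-life the ratios are 1.23 and 1.46. If the 24-hour level is unmeasurable, AUClast ends at 8 h and the bias disappears.

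It would go too far to call the whole Day 1 PK data set invalid. Cmax, Tmax and AUC0-8 still describe a single dose, provided that the TID 8-hour sample precedes the second dose. The MTD rule and the sample size are untouched.

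**What to change.** In Sections 11.1.2.1 and 14.3.9:

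- State that Day 1 single-dose parameters use only samples drawn before the second dose.
- Make AUC0-8 the exposure measure for Day 1 versus Day 7 and for comparisons between cohorts.
- Summarise the Day 1 24-hour sample as a trough only.
- Use the TID 8-hour sample only if recorded times show that it preceded the second dose. Its ±30-minute window (Section 11.4.3) straddles that dose.
- Report Day 1 AUCinf and half-life only when supported by points up to 8 h, with the percentage extrapolated.
- For Day 7 BID AUCtau, keep using the pre-dose or Day 8 12-hour trough, under a stated steady-state assumption.

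The Synopsis, Sections 11.6.1 and 11.6.2.1 and Table 7 should be reconciled on Day 1 dosing and on the label of the 24-hour sample. The diary period in Section 11.6.2.1 (Days 2 to 7) should be reconciled with Section 10.2.1, which asks for the time of every suppository, because the truncation rule needs the time of the second Day 1 dose.

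The cost is wording, with no new samples. The downside is that Day 1 AUCinf and half-life will be available for fewer patients, and may be largely extrapolated or biased if elimination or absorption is slow.

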11.6.2.2 Days 7 and 8 (± 1 day) Only for Dose Escalation

- On Day 7, assess and review TEAEs (Section [16](#)).
- On Day 7, collect urine and fasting blood samples for clinical laboratory tests ([Table 3](#)).
- On Day 7, perform a physical examination (including weight; Section [11.4.2.2](#)).
- On Day 7, administer questionnaires BPI-SF, EORTC QLQ-FA12 and Suppository Acceptance Questionnaire (SAQ).
- On Day 7, review treatment log (diary) and assess dosing compliance.
- On Day 7, review and record concomitant medications (Section [10.4](#)).
- On Day 7, collect blood samples for BNP, troponin 1, chemokines, cytokines and immunoassays prior to NOX66 administration.
- On Day 7, measure vital signs (blood pressure, pulse [radial or brachial (to be measured over 30 seconds if performed manually)], respiration rate and body temperature [oral or aural]; Section [11.4.2.1](#)) prior to NOX66 administration.
- On Day 7, administer the morning dose of NOX66 in the clinic.
- On Day 7, 12-lead ECGs will be performed in triplicate at -0.75, -0.5 and -0.25 hours prior to and at 1, 2, 5, and 8 hours post morning dose of NOX66. Holter monitoring will run from 8 to 24 hours post morning dose of NOX66.
- On Day 7, PK blood sampling pre dose and at 1, 2, 3, 4, 6, and 8 hours post application.
- On Day 8, PK blood sampling at 8 or 12 hours after the last dose of NOX66 on Day 7 for those on a TID or BID regimen, respectively. These samples may be obtained by a visiting healthcare professional at home or in the clinic.

11.6.2.3 Days 9-12 (Rest Period) Only for Dose Escalation

- Document measurable tumor lesions with CT or MRI (no need to repeat if the previous scan was within 28 days prior to Cycle 1 Day 1).
- Assess and review TEAEs (Section [16](#)).
- Review and record concomitant medications (Section [10.4](#)).

11.6.2.4 Cycle 1

- On Day 1 collect blood for BNP and troponin I prior to administration of NOX66.
- On Day 1, perform a physical examination (including weight, Section [11.4.2.2](#)).
- On Day 1 administer questionnaires BPI-SF, EORTC QLQ-C30 and EORTC QLQ-FA12.
- On Day 1, collect urine and fasting blood samples for clinical laboratory tests prior to the first dose of NOX66 ([Table 3](#)). Prior to the start of the cycle, the patient must have a minimum ANC of $1000/\mu\text{L}^3$. On Days 9 and 16, obtain hematology and clinical chemistry values to determine if any dose-reduction or delay in doxorubicin may be needed for the next dose.
- Dose Expansion only: Females of childbearing potential will undergo a urine pregnancy test prior to dosing. A window of -1 day is acceptable.
- On Day 1, dispense sufficient supply of study drug for 7 days administration.
- On Day 1 administer the appropriate number of NOX66 suppositories/per day per assigned dose cohort and instruct the patient to take the appropriate number of suppositories on Days 2-7.
- On Day 2, measure vital signs (blood pressure, pulse [radial or brachial (to be measured over 30 seconds if performed manually)], respiration rate [to be measured over 60 seconds], and body temperature [oral or aural]; prior to the dose of doxorubicin (Section [11.4.2.1](#)).
- On Day 2, administer doxorubicin (75 mg/m^2) over 15 minutes (or as per standard of care) at approximately 1 hour after administration of NOX66.
- On Day 2, 12-lead ECGs will be performed in triplicate at -0.75, -0.5 and -0.25 hours prior to and at 1, 2, 5, and 8 hours post morning dose of NOX66. Holter monitoring will run from 8 to 24 hours post morning dose of NOX66.
- On Day 2, PK samples are to be collected at within 15 minutes prior to NOX66 and at 1 and 2 hours (Dose Escalation only) and at 4 and 6 hours (Dose Expansion Cohort) after NOX66 administration and assayed for idronoxil and metabolites. PK samples will also be obtained at 0.5, 4 and 6 hours after the end of the doxorubicin infusion and assayed for doxorubicin and doxorubicinol.
- PK samples will be obtained within 15 minutes prior to the last morning dose of NOX66 on Day 7 (Dose Escalation and Dose Expansion Cohorts). These samples can be collected at the patients' home.
- On Day 8 PK samples will be obtained at 8 or 12 hours after the last dose of NOX66 for those on a TID or BID, regimen, respectively (Dose Escalation Cohorts). These samples can be collected at the patients' home or in the clinic.
- Review and record concomitant medications (Section [10.4](#)).
- Assess and review TEAEs (Section [16](#)).
- On Day 1, for those patients in the Dose-Expansion Cohort, blood samples for genetic mutations, BNP, troponin I, cytokines, chemokines and immunoassays will be obtained prior to the first dose of NOX66, if not already collected at Screening.
- Echocardiography should be repeated prior to the first dose of doxorubicin if, after the first screening echocardiograph, a patient has clinical symptoms that may indicate worsening cardiac function.

11.6.2.5 Cycle 2

- On Day 1 review treatment log, collect unused study drug, and assess compliance, from previous cycle. If needed, patients may be counseled to about being compliant with study drug.
- On Day 1, perform a physical examination (including weight, Section [11.4.2.2](#)).
- On Day 1 administer questionnaires BPI-SF, EORTC QLQ-C30, EORTC QLQ-FA12, and SAQ.
- On Day 1, collect urine and fasting blood samples for clinical laboratory tests prior to the first dose of NOX66 ([Table 3](#)). Prior to the start of the cycle, the patient must have a minimum ANC of $1000/\mu\text{L}^3$. On Days 9 and 16, obtain hematology and clinical chemistry values to determine if any dose-reduction or delay in doxorubicin may be needed for the next dose.
- On Day 1, dispense sufficient supply of study drug for 7 days administration.
- On Day 1 administer the appropriate number of NOX66 suppositories/per day per assigned dose cohort and instruct the patient to take the appropriate number of suppositories on Days 2-7.
- On Day 2, measure vital signs (blood pressure, pulse [radial or brachial (to be measured over 30 seconds if performed manually)], respiration rate [to be measured over 60 seconds], and body temperature [oral or aural]; prior to the dose of doxorubicin (Section [11.4.2.1](#)).
- On Day 2, administer doxorubicin ($75 \text{ mg}/\text{m}^2$) over 15 minutes (or as per standard of care) at approximately 1 hour after administration of NOX66.
- On Day 2, triplicate 12-lead ECGs will be obtained after 5 minutes of rest in the supine position at -0.75, -0.5 and -0.25 hours prior to and at 1, 2, 5, and 8 hours post application of NOX66.
- On Day 2, PK samples are to be collected within 15 minutes prior to the morning dose of NOX 66 administration (8 or 12 hours after the last dose of NOX66 on Day 1) and at 4 hours post NOX66 administration and will be assayed for idronoxil and metabolites.
- On Day 2, PK samples are to be collected at 0.5 and 4 hours after the end of the doxorubicin infusion and assayed for doxorubicin and doxorubicinol.
- Review and record concomitant medications (Section [10.4](#)).
- Assess and review TEAEs (Section [16](#)).
- On Day 21, assess tumor response by CT or MRI.

11.6.2.6 Cycle 3

- On Day 1 review treatment log, collect unused study drug, and assess compliance, from previous cycle.
- On Day 1, perform echocardiography (Section [11.4.2.3](#)).
- On Day 1, collect blood for BNP, troponin 1, cytokines, chemokines and immunoassays prior to administration of NOX66.
- On Day 1, perform a physical examination (including weight, Section [11.4.2.2](#)).
- On Day 1 administer questionnaires BPI-SF, EORTC QLQ-C30, EORTC QLQ-FA12, and SAQ.
- On Day 1, collect urine and fasting blood samples for clinical laboratory tests prior to the first dose of NOX66 ([Table 3](#)). Prior to the start of the cycle, the patient must have a minimum ANC of $1000/\mu\text{L}^3$. On Days 9 and 16, obtain hematology and clinical chemistry

values to determine if any dose-reduction or delay in doxorubicin may be needed for the next dose.

- On Day 1, dispense sufficient supply of study drug for 7 days administration.
- On Day 1 administer the appropriate number of NOX66 suppositories/per day per assigned dose cohort and instruct the patient to take the appropriate number of suppositories on Days 2-7.
- On Day 2, administer doxorubicin (75 mg/m^2) over 15 minutes (or as per standard of care) at approximately 1 hour after administration of NOX66.
- Measure vital signs (blood pressure, pulse [radial or brachial (to be measured over 30 seconds if performed manually)], respiration rate and body temperature [oral or aural]; Section [11.4.2.1](#)) prior to the dose of doxorubicin on Day 2.
- On Day 2, triplicate 12-lead ECGs will be obtained after 5 minutes of rest in the supine position at 0.25 hours prior to and at 1, 2, 5, and 8 hours post application of NOX66.
- Review and record concomitant medications (Section [10.4](#)).
- On Day 2, PK samples are to be collected at 4 hours post NOX66 administration assayed for idronoxil and metabolites.
- PK samples will be obtained just prior to the last morning dose on Day 7 (Dose-Escalation and Expansion Cohorts) and on Day 8 at 8 or 12 hours after the last dose of NOX66 on Day 7 for those on a TID or BID regimens, respectively (Dose-Escalation Cohorts only). The Day 8 samples can be collected at home or in the clinic.
- Assess and review TEAEs (Section [16](#)).

11.6.2.7 Cycle 4

- On Day 1 review treatment log, collect unused study drug, assess compliance, from previous cycle.
- On Day 1, perform a physical examination (including weight, Section [11.4.2.2](#)).
- On Day 1 administer questionnaires BPI-SF, EORTC QLQ-C30, EORTC QLQ-FA12 and SAQ.
- On Day 1, collect urine and fasting blood samples for clinical laboratory tests prior to the first dose of NOX66 ([Table 3](#)). Prior to the start of the cycle, the patient must have a minimum ANC of $1000/\mu\text{L}^3$. On Days 9 and 16, obtain hematology and clinical chemistry values to determine if any dose-reduction or delay in doxorubicin may be needed for the next dose.
- On Day 1, dispense sufficient supply of study drug for 7 days administration.
- On Day 1 administer the appropriate number of NOX66 suppositories/per day per assigned dose cohort and instruct the patient to take the appropriate number of suppositories on Days 2-7.
- On Day 2, measure vital signs (blood pressure, pulse [radial or brachial (to be measured over 30 seconds if performed manually)], respiration rate and body temperature [oral or aural]; Section [11.4.2.1](#)) prior to the dose of doxorubicin.
- On Day 2, administer doxorubicin (75 mg/m^2) over 15 minutes (or as per standard of care) at approximately 1 hour after administration of NOX66.
- On Day 2, triplicate 12-lead ECGs will be obtained after 5 minutes of rest in the supine position at -0.25 hours prior to and at 1, 2, 5, and 8 hours post morning dose of NOX66.
- On Day 2, PK samples are to be collected prior to the morning dose of NOX66 administration (8 or 12 hours after the last dose of NOX66 on Day 1) and 4 hours post NOX66 administration and assayed for idronoxil and metabolites.

- On Day 2, PK samples are to be collected at 0.5 and 4 hours after the end of the doxorubicin infusion and assayed for doxorubicin and doxorubicinol.
- Review and record concomitant medications (Section [10.4](#)).
- Assess and review TEAEs (Section [16](#)).
- On Day 21, assess tumor response by CT or MRI.

11.6.2.8 Cycle 5

- On Day 1 review treatment log, collect unused study drug, assess compliance, from previous cycle.
- On Day 1, perform echocardiography (Section [11.4.2.3](#)).
- On Day 1 collect blood for BNP and troponin 1 prior to administration of NOX66.
- On Day 1 perform a physical examination (including weight, Section [11.4.2.2](#)).
- On Day 1 administer questionnaires BPI-SF, EORTC QLQ-C30, EORTC QLQ-FA12 and SAQ.
- On Day 1, record ECOG status.
- On Day 1, collect urine and fasting blood samples for clinical laboratory tests prior to the first dose of NOX66 ([Table 3](#)). Prior to the start of the cycle, the patient must have a minimum ANC of $1000/\mu\text{L}^3$. On Days 9 and 16, obtain hematology and clinical chemistry values to determine if any dose-reduction or delay in doxorubicin may be needed for the next dose.
- On Day 1, dispense sufficient supply of study drug for 7 days administration.
- On Day 1, administer the appropriate number of NOX66 suppositories/per day per assigned dose cohort and instruct the patient to take the appropriate number of suppositories on Days 2-7.
- On Day 2, measure vital signs (blood pressure, pulse [radial or brachial (to be measured over 30 seconds if performed manually)], respiration rate and body temperature [oral or aural]; Section [11.4.2.1](#)) prior to the dose of doxorubicin.
- On Day 2, administer doxorubicin ($75 \text{ mg}/\text{m}^2$) over 15 minutes (or as per standard of care) at approximately 1 hour after administration of NOX66.
- On Day 2, triplicate 12-lead ECGs will be obtained after 5 minutes of rest in the supine position at -0.75, -0.5 and -0.25 hours prior to and at 1, 2, 5, and 8 hours post morning dose of NOX66.
- On Day 2, PK samples are to be collected at 4 hours post NOX66 administration assayed for idronoxil and metabolites.
- PK samples will be obtained just prior to the last morning dose on Day 7 (all cohorts) and on Day 8 at 8 or 12 hours after the last dose of NOX66 on Day 7 for those on a TID or BID regimens, respectively (Dose-Escalation Cohorts). The Day 8 samples can be collected at home or in the clinic.
- Review and record concomitant medications (Section [10.4](#)).
- Assess and review TEAEs (Section [16](#)).

11.6.2.9 Cycle 6

- On Day 1 review treatment log, collect unused study drug, assess compliance, from previous cycle.
- On Day 1, perform a physical examination (including weight, Section [11.4.2.2](#)).
- On Day 1 administer questionnaires BPI-SF, EORTC QLQ-C30, EORTC QLQ-FA12, and SAQ.

- On Day 1, collect urine and fasting blood samples for clinical laboratory tests prior to the first dose of NOX66 ([Table 3](#)). Prior to the start of the cycle, the patient must have a minimum ANC of $1000/\mu\text{L}^3$. On Days 9 and 16, obtain hematology and clinical chemistry values.
- On Day 1, dispense sufficient supply of study drug for 7 days administration.
- On Day 1, administer the appropriate number of NOX66 suppositories/per day per assigned dose cohort and instruct the patient to take the appropriate number of suppositories on Days 2-7.
- On Day 2, measure vital signs (blood pressure, pulse [radial or brachial (to be measured over 30 seconds if performed manually)], respiration rate and body temperature [oral or aural]; Section [11.4.2.1](#)) prior to the dose of doxorubicin.
- On Day 2, administer doxorubicin (75 mg/m^2) over 15 minutes (or as per standard of care) at approximately 1 hour after administration of NOX66.
- On Day 2, triplicate 12-lead ECGs will be obtained after 5 minutes of rest in the supine position at- 0.25 hours prior to and at 1, 2, 5, and 8 hours post morning dose of NOX66.
- On Day 2, PK samples are to be collected at pre-dose of NOX66 administration and at 4 hours post NOX66 administration and assayed for idronoxil and metabolites.
- On Day 2, PK samples are to be collected at 0.5 and 4 hours after the end of the doxorubicin infusion and assayed for doxorubicin and doxorubicinol.

The following assessments are required at Cycle 6 Day 21, or at Early Termination if the patient discontinues the study during the treatment period:

- Collect blood for BNP, troponin 1, immunoassays, cytokines, chemokines and genetic mutation,
- Assess tumor response with CT or MRI.
- Perform a physical examination (Section [11.4.2.2](#)).
- Measure vital signs (blood pressure, pulse [radial or brachial (to be measured over 30 seconds if performed manually)], respiration rate [to be measured over 60 seconds], and body temperature [oral or aural] (Section [11.4.2.1](#)).
- Collect urine and fasting blood samples for clinical laboratory tests (Section [11.4.2.4](#)).
- Administer questionnaires BPI-SF, EORTC QLQ-C30, EORTC QLQ-FA12 and SAQ.
- Perform echocardiography (Section [11.4.2.3](#)).
- Review treatment log, collect unused study drug, and assess compliance.
- Review and record concomitant medications (Section [10.4](#)).
- Assess and review TEAEs (Section [16](#)).

